9.2.3 Assessment of Other Outcomes of Interest

- The Childhood Trauma Questionnaire – short version CTQ-SV is a 25-item self-report scale that aims to detect experiences of childhood abuse and neglect in adults and adolescents. The Olweus Bully/Victim Questionnaire (BVQ) is a questionnaire which assesses bullying behaviour and victimization in children and adolescents, and can be filled in online. While the victimization part will be administered for all patients, the bullying part is optional. Patients who are already participating in the trial will be asked whether they agree to additionally fill in the two questionnaires, irrespective of how long they already have been participating in the trial.
- Tanner Criteria [247] Self-report form on pubertal status. The assessment of the pubertal status will enable us to investigate if the developmental stage has an impact on omega-3 fatty acids effects. If the children are > 13 years of age, parents are asked to fill in the questionnaire due to the explicit nature of the pictures.
- The Omega-3 Food Frequency Questionnaire n-3 FFQ [248] is a 21-item self-report that was developed using the National Cancer Institute's Diet History Questionnaire as a model. The scale was adapted to reflect local fish intake and was developed in conjunction with [name] of the ETH. The n-3 FFQ takes 10 minutes to complete, and assesses the average n-3 intake over the last 6 months. Items in the n-3 FFQ included an extensive list of specific seafood and fish available in Switzerland, as well as walnuts, flaxseed, flaxseed oil, cod liver oil and canola oil. The questionnaire also includes specific questions about type and dosage of n-3 PUFA dietary supplements (individuals taking supplements will be excluded).

- The WHO Assist 3.0 [249] is a widely used structured Interview to quantify substance and drug abuse that will be completed by the research interviewer enabling us to control for substance misuse.
- The Antidepressant Side Effect Checklist (ASEC) [250] is a 21-item self-report scale quantifying the most commonly described side-effects of antidepressants. It has a 0-3 scoring (0 = absent, 1 = mild, 2 = moderate, 3 = severe) and asks the patients if he believes that there is a link with the study medication for each item.

9.2.4 Assessment of Safety Outcomes

9.2.4.1 Adverse Events

The investigator controls weekly if any AE or SAE has occurred. If so, the investigator contacts the clinician to get informed about the circumstances which led to the AE, and together with the principal investigator the connection between the AE and the study drug is clarified. If a connection has been established, the SUSAR will be reported according to the principles stated in Section 10. Furthermore, at each study visit, the Antidepressiva side effect Self Report Scale (ASEC) will be administered. In case the patient reports any abnormalities, the investigator will inform the clinician and principal investigators to determine whether an AE or SAE occurred. A detailed description of collaboration and responsibilities between researchers and clinicians can be found in the SOP (collaboration between research and clinic).

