6.4 Unblinding Procedures (Code break)

An Emergency Code Break will be available through SecuTrial®. The only person authorised to unblind a patient is the sponsor-investigator [name], and the two principal investigators Prof. [name] and Prof. [name] who can do so in case of an emergency unblinding, e.g. in case of a Suspected Unexpected Serious Adverse Reaction (SUSAR). The unblinding procedure can be triggered by SecuTrial®. Once a patient is unblinded by SecuTrial®, all users of the software will know the patient's assigned treatment group and the unblinding procedure cannot be reversed. Therefore, the participant will be considered a drop-out. A drop-out visit will be performed in a clinically meaningful time frame.

Emergency unblinding is indicated in the following situations:

- Unblinding is necessary for the subjects emergency treatment at the clinicians or investigator's discretion.
- Unblinding is required by local laws or regulations (in case of SUSAR).
- The IDMC decides that unblinding is necessary for proper study management of the subjects and the overall safety of the other subjects in the study.

After closing of the database every site will be informed about each subject's assigned treatment group.

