7.4 Criteria for Withdrawal/ Discontinuation of Participants

Clinicians/ treating doctors/ patients and their relatives can withdraw a patient at any time if they think it is in his best interest. To support clinicians in their decision making at what point a patients shall be withdrawn from the study for safety reasons, we defined following exit criteria.

Reasons to terminate a subject's participation:

- A subject withdraws her/his consent
- Non-compliance with medication (no intake of study medication for more than three out of seven days in two consecutive weeks)
- Daily omega-3 supplementation in addition to study medication (>600 mg combined EPA/DHA per day for more than one week)
- The clinician or investigator considers a subject's continued participation in the study to be unjustifiable on medical grounds (i.e. because of the emergence of another serious medical condition).
- The subject falls below a score of 40 on the Children's Depression Rating Scale at the end of the placebo lead-in phase.
- Acute Suicidality/ overt hostility: Clinicians and research assistants will monitor suicidality/hostility at each visit. If a clinician/ researcher considers the suicidal risk/ hostility as high requiring some sort of clinical action (e.g. a suicide watch plan as an outpatient, or restricted leave as an inpatient because of intense suicidal ideation/hostility), patients shall be withdrawn from the study if the clinician considers a potential connection with the study drug and a SUSAR shall be reported. The number and type of SUSARs will be compared between the treatment groups (active versus placebo).
- Intolerance to the study drug. Life-threatening side effect other than suicidality/ hostility (SUSAR): In case of an unexpected life-threatening side effect (e.g. a severe allergic reaction to one of the ingredients of the study medication), a patient must be withdrawn from the study.
- The development of a major axis one disorder listed under the exclusion criteria (e.g. a first psychotic or manic episode is considered as a serious adverse event).
- Unwanted but not life-threatening adverse events: If the side effect persists, the study medication shall be ceased and the patient discontinued due to lack of tolerability (an important further outcome criteria).

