Any other medically important condition that may be not immediately life-threatening or results in death or hospitalization but may jeopardize the participant or may require intervention to prevent one of the outcomes listed above should also usually (i.e. based on medical and scientific judgment) be considered serious. For example: intensive treatment at home for allergic bronchospasm; certain laboratory abnormalities (e.g. blood dyscrasias); convulsions that do not result in hospitalisation; development of drug dependency.

SAEs should be followed until resolution or stabilisation. Participants with ongoing SAEs at study termination (including safety visit) will be further followed up until recovery or until stabilisation of the disease after termination.

Unexpected Adverse Drug Reaction

An "unexpected" adverse drug reaction is an adverse reaction, the nature or severity of which is not consistent with the applicable product information (e.g. Investigator's Brochure for drugs that are not yet approved and Product Information for approved drugs, respectively).

Suspected unexpected serious adverse reaction (SUSAR)

A serious adverse reaction, the nature or severity of which is suspected to be not consistent with the applicable product information as stated in the Investigator's Brochure.

Safety Signals

All suspected new risks and relevant new aspects of known adverse reactions that require safety-related measures.

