5.2.2 Supportive secondary endpoints

Effect endpoints

- Number of days in hospital
- Lower outpatient service use

Safety endpoints

- Suicidal ideation (SIQ-Jr) from baseline to week 36 (measured at baseline, 6, 12, 24, and 36 weeks)
- Number of SUSARs from baseline to week 36

Statistical considerations

6 Sample size determination

The sample size calculations were performed for the primary outcome, as well as closely related secondary outcomes in order to ensure all questions of high interest are sufficiently powered. All calculations assume a parallel two-arm design with a 1:1 randomization ratio.

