7.2.2 Supportive secondary endpoints

Effect endpoints

- **Number of days in the hospital**
- **Outpatient service use**

These endpoints will be described using summary statistics across treatment arm.

Safety endpoints

- **Suicidal ideation** from baseline to week 36 will be modeled jointly by a linear mixed effects model for SIQ-Jr score over time combined with Cox regression for time to intervention and study dropout, analogously to the CDRS-R total score primary outcome model.
- **Serious adverse events** from baseline to week 36 will be tabulated per type and treatment arm using the safety analysis set. If appropriate, the difference in proportion (with 95% confidence interval) will be estimated.

8 Changes to the statistical analyses planned in the protocol

Version	Explanation
IICT submission	First version of study plan
Frontiers protocol	Study protocol after funding review and peer review, addition of concomitant treatment description, addition minimization factor for unit type (in-/outpatient), description of sensitivity analyses to account for antidepressant use
UZH protocol	Refinement of secondary (supportive/exploratory) outcomes and their analyses
Statistical analysis plan	Focusing the analysis plan on measures of efficacy and safety for reporting of primary trial results. Updating method for dealing with informative missingness.

9 References

N. M. Laird and J. H. Ware. Random-effects models for longitudinal data. *Biometrics* 1982; 38:963–74

R J A Little and L Yau. Intent-to-treat analysis for longitudinal studies with drop-outs. *Biometrics* 1999; 52:1324–33.

S Mazumdar and K S Liu and P R Houck and C F Reynolds. Intent-to-treat analysis for longitudinal clinical trials: coping with the challenge of missing values. *Journal of Psychiatric Research* 1999; 33:87–95

Michele L Shaffer and Vernon M Chinchilli. Including multiple imputation in a sensitivity analysis for clinical trials with treatment failures. *Contemporary Clinical Trials* 2007 28:130–137

Ian R. White and C Bamias and P Hardy and S. Pocock and J Warner. Randomized clinical trials with added rescue medication: some approaches to their analysis and interpretation. *Statistics in Medicine* 2001; 20:2995–3008.

R version and packages used to generate this report:

R version: R version 4.0.1 (2020-06-06)

Base packages: stats, graphics, grDevices, utils, datasets, methods, base

Other packages: pwr, readxl, reporttools, xtable, knitr

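### The SUSAR label follows inconsistent criteria across the protocol, the SAP lists a SUSAR endpoint that it does not analyse, and a code break for a SUSAR is visible to every SecuTrial user

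*Protocol*

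**What the plan says.** **Definition.** Protocol 10.1 defines a SUSAR as "A serious adverse reaction, the nature or severity of which is suspected to be not consistent with the applicable product information" in the Investigator's Brochure. Protocol 10.4 reports SUSARs on the same basis: an SAE judged suspected, unexpected and drug related.

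**Other uses of the label.** Protocol 9.2.4.1 opens with "The investigator controls weekly if any AE or SAE has occurred". It has the investigator, the clinician and the principal investigator settle whether the event is connected with the study drug, and then states: "If a connection has been established, the SUSAR will be reported according to the principles stated in Section 10". In Protocol 7.4, where suicidal risk or hostility is judged high enough to need clinical action, "patients shall be withdrawn from the study if the clinician considers a potential connection with the study drug and a SUSAR shall be reported". A second 7.4 item carries the label in its title, "Life-threatening side effect other than suicidality/ hostility (SUSAR", but its text is limited to unexpected life-threatening effects.

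**Code break.** Protocol 6.4 gives a SUSAR as its example of emergency unblinding, and lists it again where local law or regulation requires unblinding. On the consequences of a code break it reads: "all users of the software will know the patient's assigned treatment group and the unblinding procedure cannot be reversed. Therefore, the participant will be considered" (the sentence ends by giving drop-out status).

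**Endpoint and analysis.** Protocol 7.4 says that the number and type of SUSARs will be compared between arms. Protocol 5.4 (WH 5a) hypothesises no drug-related SUSARs, and Protocol 11.4.3 plans a two-proportion z-test. SAP 5.2.2 lists "Number of SUSARs from baseline to week 36". SAP 7.2.2 has no SUSAR entry. It names serious adverse events, which "will be tabulated per type and treatment arm using the safety analysis set".

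**The concern.** A safety endpoint needs one case definition. Here the same event could be a SUSAR under one section and an ordinary AE under another, so the count could depend on which section a site reads. The SAP then leaves open which quantity is reported under the endpoint.

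The label also bears on blinding. If a SUSAR leads to a code break that every database user can see, research staff may learn a child's arm before rating that child again.

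**Working it through.** No figure in the plan needs reproducing. The check sets the passages side by side.

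**1. Criteria attached to the label**

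| Protocol section | Serious? | Unexpected? | Drug link |
|---|---|---|---|
| 10.1, 10.4 | required | required | drug related |
| 9.2.4.1 | not stated; starts from AE or SAE | not stated; reporting referred to Section 10 | connection established |
| 7.4, suicidality or hostility | not stated; high risk needing clinical action | not stated | potential connection |
| 7.4, life-threatening effect | life-threatening | required | side effect of study drug |

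The last row fits within 10.1. The second and third do not state its criteria. Section 7.4 also treats persistent adverse events that are not life-threatening as lack of tolerability and does not call them SUSARs, so 9.2.4.1 read literally disagrees with 7.4 as well. Under 10.3 an event is related if its timing is plausible and it cannot be definitely explained otherwise. That is an easy test to meet during 36 weeks of daily dosing. The protocol states no order of precedence among these sections.

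**2. What is counted.** Three quantities could be reported: events meeting 10.1, events labelled under 9.2.4.1 or 7.4, and all SAEs (SAP 7.2.2). The SAE table includes unrelated and expected events, so SUSARs cannot be read from it. It also excludes any non-serious event labelled under 9.2.4.1. The lists of changes in SAP sections 2 and 8 mention no move from SUSARs to SAEs.

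**3. Who would see a code break.** Section 6.4 says all software users. Under 13.2, research assistants and local investigators enter data in SecuTrial, and under 9.2.1 the research interviewer rates the CDRS-R. The drop-out visit includes the CDRS-R and the K-SADS-PL (8.5, 9.2.4.3). Against this, 6.3.1 says research assistants, clinicians and all researchers remain blind, and names the CTC data manager and the trial pharmacist as the only holders of the code. Section 11.3 says that among researchers only the IDMC has unblinded access to SecuTrial. These three sections cannot all hold after a code break run through SecuTrial.

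**4. Sensitivity of a small count (illustration only).** The documents give no SUSAR rate, so the counts here are assumed. With 110 per arm (synopsis) and *a* versus *b* participants with an event:

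p = (a + b)/220; SE = √[p(1 − p) × 2/110]; z = [(a − b)/110]/SE.

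- 4 versus 0: p = 0.01818, SE = 0.01802, z = 0.03636/0.01802 = 2.018, two-sided p-value 0.0435 (Fisher's exact test 0.1216).
- One mislabelled event added to each arm, 5 versus 1: p = 0.02727, SE = 0.02196, z = 1.656, p-value 0.0978.
- Two added to each arm, 6 versus 2: p-value 0.1497, and the ratio is 3.0.

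A few classification differences can therefore change the comparison planned in Protocol 11.4.3. This does not show that such events occurred.

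**The case against.** The case on the other side has substance.

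- **Section 9.2.4.1 may be shorthand.** It sends reporting to Section 10, where the study doctor classifies events and 10.1 and 10.4 apply the usual criteria. A strict reader could let Section 10 govern. This weakens the conflict without removing it, because 9.2.4.1 has already called the event a SUSAR and 7.4 contains no such reference.
- **The 7.4 events may be serious.** Section 10.1 includes events that may jeopardise the participant or require intervention, which plausibly covers high suicidal risk. Whether they are unexpected depends on the Investigator's Brochure, which is not among the documents. What stands is that 7.4 does not ask the question.
- **The code break is not automatic.** A reader might infer that every drug-related complaint becomes a SUSAR, is unblinded and ends follow-up. Assumed rates of 2%, 5% or 10% would then give 110 × 0.02 = 2.2, 110 × 0.05 = 5.5 or 110 × 0.10 = 11 code breaks on active. The documents do not support this. Section 6.4 lets only three roles unblind, says that they can do so, and ties the listed SUSAR indication to legal requirement. The rates are not documented, and neither is an excess on active. Some of these participants would leave anyway under the other 7.4 withdrawal texts.
- **Harm to the primary outcome.** A reader might infer that unblinded ratings enter the CDRS-R model. SAP 5.1 and 7.1 use baseline and weeks 6, 12, 24 and 36, and no section says that the drop-out-visit score is used.
- **Corruption of the SAP safety result.** An SAE table would not absorb mislabelled non-serious events, so the exposure is confined to the SUSAR count and the protocol's z-test.

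**Conclusion.** The concern holds as an inconsistency of definition, endpoint and blinding procedure. The SUSAR criteria in Protocol 9.2.4.1 and 7.4 are not those of 10.1 and 10.4. SAP 5.2.2 names an endpoint for which 7.2.2 gives no analysis, and this mismatch stands however the label is read. Section 6.4 conflicts with 6.3.1 and 11.3 on who sees the allocation after a code break.

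The size cannot be computed from the documents. The p-value shifts rest on assumed counts with equal additions to each arm. Bias in the primary CDRS-R analysis is not shown. The point is worth correcting because the remedy is cheap and protects both the blinding and the safety comparison.

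**What to change.** 1. In Protocol 9.2.4.1 and 7.4, record events as AE or SAE with causality, and classify as a SUSAR only when the 10.1 criteria are met. Re-check any SUSAR already reported against 10.1, blind to arm.
2. Route regulatory unblinding for a SUSAR through the code holders already named in 6.3.1 (trial pharmacist or CTC data manager), outside the SecuTrial view open to sites. Reconcile 6.4 with 6.3.1 and 11.3.
3. Flag any CDRS-R rated after a visible code break.
4. Make SAP 5.2.2 and 7.2.2 match: SAEs by arm, with SUSARs by the 10.1 definition as a reported subset.

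The withdrawal and drop-out texts in 6.4, 7.4 and Section 10 must be reconciled by the sponsor. No clinical rule is proposed here.

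The cost is a wording amendment, a short blinded re-classification and, for each regulatory code break, a call to the code holder. No new patients or visits are needed. The protocol projected the last participant out for 31.03.2022 and the SAP is dated May 23, 2022. If that date was kept, item 2 comes too late for this trial's follow-up, but the re-check in item 1 and items 3 and 4 can still be done before reporting.

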9.2.4.2 Laboratory Parameters

At screening and at nine months (or the drop out visit), blood will be drawn for standard clinical laboratory tests. Clinical blood parameters (haemoglobin, haematocrit, leucocytes, thrombocytes, TSH (thyroid function test), ALAT & ASAT (liver function test), and thromboplastin (blood coagulation) will be assessed in order to screen the patient for abnormal blood parameters. These analyses will be done in the Children's hospital of Zurich. The results will be entered into the eCRF as they are part of the inclusion criteria and will also provide the stratification parameter (hSRF). All the other blood samples will be stored for analyses as outlined in the protocol.

9.2.4.3 Vital Signs

Vital signs will be assessed in the lead-in phase and again at the end of the study (week36) by the study nurse or investigator (e.g. heartbeat, blood pressure, body temperature, height and weight).

A drop-out visit shall be performed including documentation of reasons for drop out in case a patient drops out, or a parent / clinician / investigator withdraws a patient from the study. The drop-out visit will be performed at the earliest convenient time and will include an assessment of physical health and current medication use. Depressive symptoms will be assessed using the CDRS-R and the K-SADS-PL. In addition, psychosocial functioning will be assessed with a range of clinician rated scales (CGI-S/I, CGAS, HoNOSCA) and self-reported scales (DIKJ, BHS, BAI II, SIQ-Jr, PSS-10, Connor-Davidson Resilience Scale, SDQ, Insomnia Severity Index, IES-27-J). Patients will fill in the ASEC for assessing putative side effects. If the patient agrees, blood, urine, saliva and hair will be sampled, and in case no IQ test was done previously during the trial, a short IQ test will be performed.

9.3 Procedures at Each Visit

9.3.1 Screening and lead-in phase

During the first meeting with the investigator or psychologist, the study will be explained to the subject including possible benefits and disadvantages of participation. When the patient's willingness is assured and written informed consent is provided, the subject will be screened for in- and exclusion criteria. Information about sociodemographic, medical and family history, current medication use, psychiatric history, drug use, and childhood trauma will be collected. Current and past episodes of psychopathology will be determined using the semi-structured diagnostic interview Schedule for Affective Disorders and Schizophrenia for School Aged Children (K-SADS-PL) in cases where no K-SADS-PL interview has been done in the last 4 weeks. If a K-SADS-PL interview has already been performed in the last 4 weeks in the context of standard clinical praxis, the K-SADS-PL shall not be repeated given the extensive nature of the full interview. In that case, the results should be transferred from the clinical records into the study database. The Children's Depression Rating Scale (CDRS-R) is used to determine severity of depressive symptoms.

The K-SADS and the CDRS are both completed once with the patient and once with a parent / caregiver. At the time of the appointment with the parents, also the other parent-rated questionnaires (PTBS Checklist, BRIEF-E, SDQ-E, KIDscreen-Cat-E, IES27-E) shall be administered so that only one appointment in the first week with the parent is necessary. Alternatively, these questionnaires can also be filled in online (via a unique SecuTrial access code) by the parents any time prior baseline. The interview with the patient may be at the same time or at a different time, depending on the convenience and age of the patient. Research assessments may be carried out either at the participating centres or at the patients' home, as wished by the patients and their families.

Thereafter the patient enters the single-blind, placebo lead-in period (7 to 10 days). The capsules may be given to the patient any time before baseline but the duration of the intake of the placebo lead in capsules should not exceed 12 days. The lead in phase is single blind, meaning that the patient and parents do not know that the participants takes placebo capsules during the lead in phase. The research interviewer will also schedule further appointments prior to baseline to sample biological variables and further assess psychosocial and cognitive functioning. Similar to the questionnaires and the cognitive testing, biological sampling can take place any time before baseline but not thereafter.

To minimise the burden for participants, blood to assess levels of bioactive lipids, (epi)genetic markers and immune parameters will be collected simultaneously. In addition, a physical examination will be conducted where heart rate, blood pressure, weight, height and body temperature will be measured. Cognitive testing will be performed anytime during the lead-in phase but before baseline and a short questionnaire regarding executive functioning (BRIEF) will be filled in. The current dietary intake of Omega-3 fatty acids will be assessed with the FFQ. An appointment for the baseline visit will be scheduled.

